8.1.4 Vital Signs

Vital signs include temperature, systolic and diastolic blood pressure, and pulse rate will be measured at the Screening Visit and at the End of Study Visit. Unscheduled vital signs may be measured as clinically necessary and shall be reported in the subject's eSource/eCRF form. Height and body weight will be measured at the Screening Visit only.

8.1.5 Nasal Mucosal Examination

A nasal mucosal examination will be performed at the Screening Visit and at the End of Study Visit to determine presence of polyps, nasal passage redness, deviated septum, purulence or other abnormalities. Subjects with the presence of any of these that are considered clinically significant prior to enrollment at the Screening Visit will be excluded from participation in the study. The results of the examination shall be reported in the subject's eSource/eCRF. Clinically significant changes that are noted at the End of Study Visit and/or during an unscheduled nasal mucosal examination will be recorded as an AE on the AE eCRF. If significant abnormalities are found, then the subject may be referred to an ear, nose and throat specialist.

8.1.6 Urine Pregnancy Test

Female subjects of childbearing potential will be given a urine pregnancy test at the Screening Visit and at the End of Study Visit. Subjects with a positive urine pregnancy test will be excluded or withdrawn from the study.

8.1.7 Enrollment

Subjects who sign the informed consent form, complete all screening evaluations, and meet the eligibility criteria outlined in Sections 6.1 and 6.2 will be eligible for enrollment into the study.

8.1.8 Training

A member of the study site personnel, the trainer, will train enrolled subjects on the following:

- How to complete the headache-related symptom assessments and enter the nasal CO₂ administration details in eDiaries
- How and when to administer the nasal CO₂ using the Directions for Use as a guide
 - This includes using the activated device one time 5 seconds/nostril
- How to enter data (e.g., to medical problems, medications/treatments, etc.) in the eDiary
- When it is acceptable to take rescue medication, if needed
- When the dispenser is operating properly (i.e., makes a hissing sound, which will be demonstrated by the trainer during the Screening Visit) and to contact the site if the dispenser is not operating properly
- Contact site if experiencing any significant AEs and, if after hours, subject should go to the emergency room

It is the responsibility of the study site personnel to ensure that each subject completely understands how to do all of these tasks. This training should be documented in the subject's eSource/eCRF documents.

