3.3.5.3 C213 (Perennial Allergic Rhinitis Multi-Dose Study)

Study C213 was a randomized, double-blind, placebo-controlled, single-center, cross-over study to evaluate the effect of nasal, non-inhaled CO₂ on nasal congestion using acoustic rhinometry in subjects with PAR. Twenty (20) subjects were randomized to receive study drug in one of four treatment sequences. Each sequence consisted of the same four treatments in different order. These four treatments were:

- Dose A: Nasal CO₂ (0.5 SLPM) for 5 sec/nostril
- Dose B: Nasal CO₂ (0.5 SLPM) for 10 sec/nostril
- Dose C: Nasal CO₂ (0.5 SLPM) for 30 sec/nostril
- Dose D: Placebo (0.0 SLPM, no gas) for 30 sec/nostril

All 20 subjects completed all four treatments and completed the study.

Protocol 15-001CA
Nasal CO₂

CO₂ was delivered via a nosepiece that was attached to a CO₂ cylinder by plastic tubing. The flow rate was controlled by a flow control valve at 0.0 SLPM for the placebo dose for (Dose D) and 0.5 (\pm 0.05) SLPM for the active doses (Doses A, B, and C).

No consistent changes in nasal congestion were seen as measured by acoustic rhinometry.

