5.2 Study Treatment

5.2.1 Dose Description

This is an open-label study so all eligible subjects will receive a nasal CO₂ hand-held dispenser. One dose will consist of a 10 second administration of nasal CO₂ to each nostril. Subjects will be instructed to use the nasal CO₂ dispenser, 10 sec/nostril, as needed up to 6 times to treat one attack. Each dose must be separated by 3-5 minutes. Subjects should treat only one attack during a 24-hour period with the investigational product. Subjects may treat up to three cluster headache attacks during the treatment phase of this study.

Subjects may receive up to a total of 1.0 L of CO₂ if they treat one attack with 6 doses. Subjects may receive a total of 3.0 L of CO₂ if they treat three headache attacks with 6 doses of CO₂ during this study.

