8.1.3 Physical Examination

A full physical exam, including all major body systems and neurological exam, will be performed at the Screening Visit and at the End of Study Visit. Any conditions or symptoms reported after the subject is enrolled will be recorded as an AE on the AE eCRF. This includes new events after nasal CO₂ administration, conditions that become more severe or increase in frequency, any disease-related signs or symptoms present at the Screening Visit (see Section 8.1.2) that have worsened in severity or frequency, as well as any event or finding that the Investigator feels is clinically significant.

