8.1.11 Adverse Events

Subjects will be monitored for safety from the time they are enrolled until the End of Study Visit.

Non-serious adverse events (NSAEs) will be collected beginning after the first dose of study medication through the End of Study Visit and will include any change from the subject's condition at Screening.

SAEs will be collected following enrollment and will include any change from the subject's baseline condition at Screening. SAE collection will conclude at End of Study or until resolution of the SAE if it extends beyond the End of Study Visit.

Subjects will be instructed to record in the eDiary any adverse events they experience from the time they are enrolled at the Screening Visit until their End of Study Visit. Any conditions or symptoms reported will be recorded as an AE in the subject's AE eCRF page. Subjects who have an ongoing AE related to study drug and/or study device will be followed until resolution or stabilization of the event.

At the End of Study Visit, subjects will be asked by the Investigator or an appropriate member of the study site personnel about any AEs they have experienced since the previous visit. All AEs recorded by the subject in the eDiary will be discussed and reviewed by the Investigator or an appropriate member of the study site personnel, recorded in the subject's source documents, and on the appropriate eCRF. Subjects will be instructed to contact the study site in the event they experience any significant AEs. At the discretion of the Investigator, the subject may be asked to come to the study site for an Unscheduled Visit. Additional information regarding AEs is provided in Section 9.0.

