9.3 Reporting of Safety Information

9.3.1 Adverse Event Reporting

All AEs, regardless of causality, severity, whether expected or not, must be entered on the AE CRF. Disease-related signs and symptoms that are present at baseline should not be reported as AEs unless they worsen in severity or frequency. Information collected concerning AEs will include the following:

- Name of the event
- Start date
- Stop date or if the event is continuing
- Intensity

- Mild (does not interfere with subject's usual function)
- Moderate (interferes to some extent with the subject's usual function)
- Severe (interferes significantly with subject's usual function)
- Relationship to investigational product (drug, device or both)
- Seriousness of event
- Outcome
- Action taken

Non-serious adverse events will be collected beginning after the first dose of study medication through the End of Study Visit and will include any change from the subject's condition at Screening. All NSAE that are deemed related to study drug and/or study device will be followed until resolution or stabilization of the event. SAEs will be collected following enrollment and will include any change from the subject's baseline condition at Screening. SAE collection will conclude at End of Study or until resolution of the SAE if it extends beyond the End of Study Visit.

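### Non-serious adverse events have two conflicting start points, first dose and enrolment, so reactions to the 5-second training use at Screening could go unrecorded

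*Combined protocol and SAP*

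**What the plan says.** **Training exposure.** Section 8.1.8 lists what site staff teach enrolled subjects, including how to give the gas: "This includes using the activated device one time 5 seconds/nostril". Both schedules of events (Synopsis and Section 8.2) place training at Screening only.

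**First-dose rule.** Section 8.1.11: "Non-serious adverse events (NSAEs) will be collected beginning after the first dose of study medication through the End of Study Visit". Section 9.3.1 repeats it: "Non-serious adverse events will be collected beginning after the first dose of study medication through the End of Study Visit". Both sections define the events as changes from the subject's condition at Screening.

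**Enrolment rule.** Section 8.1.11 also has subjects enter in the eDiary "any adverse events they experience from the time they are enrolled at the Screening Visit until their End of Study Visit". Section 8.1.3 says: "Any conditions or symptoms reported after the subject is enrolled will be recorded as an AE on the AE eCRF", and continues: "This includes new events after nasal CO₂ administration".

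**Dose.** Section 5.2.1: "One dose will consist of a 10 second administration of nasal CO₂ to each nostril". Section 7.1.1 agrees. No section says whether the training use counts as a dose.

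**Scheduled checks.** Both schedules mark adverse event assessment for Treatment and End of Study, not for Screening.

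**Denominator.** Section 10.4.4 takes enrolled subjects with at least one administration of product. Section 10.8 takes all enrolled subjects.

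**The concern.** The two start points would matter little if nothing happened between them. Here an exposure to the product falls in the gap. On the dose definition, the training use comes before the first dose, so the first-dose rule does not cover a sting, watering eye or nosebleed that it provokes. The enrolment rule does cover it. Which sentence a site follows then decides whether the event is recorded, and any resulting error lowers the adverse event frequency.

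Safety is half of the primary objective (Section 4.1), and local reactions at the administration site head the anticipated events in Section 3.4. These are the reactions a training use would be expected to cause.

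**Working it through.** No sample size, power or error rate is involved. The check is a short exposure calculation and a comparison of the rules.

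**1. Exposure.** Inputs: target flow 0.5 L/min (Section 5.2.1.1); 10 seconds per nostril for a dose (Section 5.2.1); 5 seconds per nostril at training (Section 8.1.8). Volume = flow × total seconds / 60.
- One dose: 0.5 × 20/60 = 0.167 L, which agrees with the Synopsis figure of 0.17 L. Six doses: 1.0 L, which also agrees.
- Training use: 0.5 × 10/60 = 0.083 L.
- Ratio: 0.083/0.167 = 0.50.

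That the training use delivers CO₂ is inferred from the word for an activated device and from the hissing sound described in Section 8.1.8. Nothing says the training device is empty.

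**2. Could a site count the training use as a dose?** Sections 5.2.1 and 7.1.1 point to no, since it is half the stated duration. The background section on an earlier rhinitis study points the other way, because it labels the same duration and flow as a dose: "Dose A: Nasal CO₂ (0.5 SLPM) for 5 sec/nostril". Either reading is open.

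**3. What each combination does to a non-serious training reaction.**

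| Start rule followed | Training use counted as a dose | Reaction within the collection period? |
|---|---|---|
| Enrolment | Yes | Yes |
| Enrolment | No | Yes |
| First dose | Yes | Yes |
| First dose | No | No |

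One of the four combinations loses the event. It is the one that takes the first-dose sentence and the dose definition at face value.

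**4. Length of the gap.** Section 5.0 allows 0 days to 12 weeks from screening to treatment, and Section 5.3 allows a further 12 weeks for a subject who has treated nothing. Section 6.3 foresees subjects who have no episode at all. For them the first-dose sentence, read alone, is never triggered.

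**5. Numerator and denominator.** A subject exposed only at training is enrolled and has plausibly had an administration, so is counted under either Section 10.4.4 or Section 10.8. The subject stays in the denominator while the event may be missing from the numerator.

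**6. Weight of one subject.** Section 10.8.1 reports adverse events above 5%. With 25 subjects, one is 1/25 = 4.0% and two are 2/25 = 8.0%, so one missing record could move an event across that line. This shows the unit of effect and does not estimate how many records would be missing.

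**The case against.** The strongest reply is that most of the protocol pushes towards capture:
- Section 8.1.11 opens by monitoring safety from enrolment, runs the eDiary from enrolment, and sends any reported symptom to the adverse event page with no first-dose condition.
- Section 8.1.3 speaks of events after administration, not after a dose.
- Sections 9.1, 9.3.1 and 10.8.1 call for all adverse events to be recorded.
- Staff are present at training and document it (Section 8.1.8).
- Calls at about 4 and 8 weeks ask about adverse events (Section 8.1.13).
- Serious events are collected from enrolment (Sections 8.1.11 and 9.3.2).

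The trial is also an open-label, single-arm pilot with no numerical safety threshold, and treated subjects may take up to 18 full doses (6 × 3). A missed mild reaction to half a dose is unlikely to change the safety conclusion.

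Most of this stands, and it is why the point is minor. It does not remove the conflict. Section 9.1 refers back to Section 8.1.11, where both rules sit. The calls ask about concerning events, and the End of Study question covers the time since the previous visit, which may be Screening itself. A brief sting is easily forgotten by then. Because changes are judged against the condition at Screening, a reaction at that visit could also be taken as baseline.

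A reader might infer that subjects who are trained but never treat an attack have no adverse event collection at all. The documents do not support that. Section 6.3 requires enrolled subjects who withdraw to attend the End of Study Visit, where an adverse event assessment is scheduled, and the eDiary and calls apply to them too.

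**Conclusion.** The conflict is in the current text and is certain. The consequence is conditional: non-serious training reactions are at risk only where a site follows the first-dose sentence and does not treat the training use as a dose. The loss is zero under every other combination, and is probably small even there. Severity is minor. The conclusion assumes that the training device delivers CO₂ at the target flow.

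A reader might infer a deficit of several percentage points in the adverse event rate by taking the 36.8% nasal discomfort in migraine study C113 and the share of migraine subjects who did not treat or did not complete. That calculation should not be used:
- The C113 rate arose with up to 4 doses in each of up to 4 headaches, so up to 16 full doses, and cannot be carried to one half-dose.
- The 48 subjects in C112 (292 − 244) are described only as not completing, not as never treating.
- Nothing links non-treatment in migraine to non-treatment in cluster headache.
- The calculation supposes that nothing at all is recorded for such subjects.

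The documents give no reaction rate for a 5-second use, so the size cannot be estimated from them.

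**What to change.** In Sections 8.1.11 and 9.3.1, start non-serious collection at the first exposure to the activated device, and state that this includes the training use. Starting at enrolment would also work and would match Section 8.1.3 and the eDiary instruction. Add an adverse event check after training to the Screening column of both schedules. List events after training, and any other events before the first attack dose, separately from events after attack doses.

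The cost is one sentence in each of two sections, one mark in a schedule that appears twice, and one listing. The reported adverse event rate may be slightly higher. If enrolment is chosen as the start, some background events unrelated to CO₂ will be recorded during a wait of up to 12 weeks or longer; the separate listing keeps them apart. Starting at first exposure shortens the wait little, because training takes place at Screening, but it ties the rule to the product.

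Aligning the safety populations in Sections 10.4.4 and 10.8 is a separate wording point and is not needed to close this gap.

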8.1.9 Subject Diary and Assessments

The primary and most of the secondary endpoint data will be collected from the electronic daily headache diary. Site personnel will be responsible for instructing subjects on the requirement for timely completion of the electronic diary. An email will be sent to subjects for completion of their headache diary containing a link to the diary. This link will take them to a survey queue

Protocol 15-001CA
Nasal CO₂

where all diaries will be available for completion. The diary for each headache should be completed during or immediately after each headache treated with nasal CO₂ and will document:

- Pain severity: (0=none, 1=mild, 2=moderate, 3=severe)
- Baseline pain severity
- Study medication usage
- Rescue medication usage
- Pain severity after initial treatment with nasal CO₂, symptoms at 5, 15, 30, and 60 minutes following treatment
- Headache resolution
- Unusual symptoms

All assessments must be completed as close as possible to the protocol-specified time of the assessment.

8.1.10 Treatment of Cluster Headaches

Subjects will be allowed to treat up to 3 cluster attacks during this study.

If subjects still have pain and/or any other symptoms after the initial dose then they may take up to 5 more doses (each dose must be separated by 3-5 minutes). Thus, subjects may take up to 6 doses of nasal CO₂ to treat a headache.

Subjects will record the details about each dose taken (i.e., time of nasal CO₂ administration, duration of administration) in the eDiary.

8.1.11 Adverse Events

Subjects will be monitored for safety from the time they are enrolled until the End of Study Visit.

Non-serious adverse events (NSAEs) will be collected beginning after the first dose of study medication through the End of Study Visit and will include any change from the subject's condition at Screening.

SAEs will be collected following enrollment and will include any change from the subject's baseline condition at Screening. SAE collection will conclude at End of Study or until resolution of the SAE if it extends beyond the End of Study Visit.

Subjects will be instructed to record in the eDiary any adverse events they experience from the time they are enrolled at the Screening Visit until their End of Study Visit. Any conditions or symptoms reported will be recorded as an AE in the subject's AE eCRF page. Subjects who have an ongoing AE related to study drug and/or study device will be followed until resolution or stabilization of the event.

At the End of Study Visit, subjects will be asked by the Investigator or an appropriate member of the study site personnel about any AEs they have experienced since the previous visit. All AEs recorded by the subject in the eDiary will be discussed and reviewed by the Investigator or an appropriate member of the study site personnel, recorded in the subject's source documents, and on the appropriate eCRF. Subjects will be instructed to contact the study site in the event they experience any significant AEs. At the discretion of the Investigator, the subject may be asked to come to the study site for an Unscheduled Visit. Additional information regarding AEs is provided in Section 9.0.

8.1.12 Concomitant Medications / Procedures

Medications taken and procedures performed, within 30 days prior to the Screening Visit will be recorded in the subject's eSource/eCRF. Medications taken after the Screening Visit and until the end of the subject's participation in the study (End of Study Visit) will be recorded by the subject in the eDiary. Any rescue medication taken will also be recorded in the subject's eDiary. At the End of Study Visit as well as at any unscheduled visits, subjects will be asked about the medications, procedures and/or alternative treatments (e.g., homeopathy, natural health products, etc.) they have taken since their previous visit. All medication and procedures including rescue medication recorded by the subject on the diary will be discussed and reviewed by the Investigator or an appropriate member of the study site personnel, recorded in the subject's eSource/eCRF.

8.1.13 Telephone Contact

Subjects will be contacted within 3 days of treating their first headache attack with nasal CO₂ to answer any questions the subject may have, to assess if there are any problems with compliance, or any concerning AEs. Furthermore, during the treatment period, approximately at 4 and 8 weeks after the Screening Visit, a member of the study site personnel will follow-up with the subject via telephone to answer any questions the subject may have, to assess if there are any problems with compliance or any concerning AEs and, as necessary, to request that the subject return to the clinic for a replacement dispenser.

If it is determined that the subject is non-compliant with the requirements of this study, then it is the Investigator's discretion whether or not to withdraw the subject from the study.

8.2 Schedule of Events

Study Procedures	Screening	Treatment	End of Study Visit ¹
Informed Consent	X		
Eligibility	X		
Medical History/ Medications / Demographics	X		
Physical Examination including Neurological and Nasal Mucosal Exam	X		X
Vital Signs	X		X
Urine Pregnancy Test	X		X
Subject Training	X		
Subject eDiary, AE/ConMed diary, and Questionnaire Instruction	X		
Investigational Product Dispensation	X	X ²	
Accountability of Investigational Product Study Drug and Study Supplies	X		X
Diary Completion		X	
Adverse Event Assessment		X	X
Concomitant Medications Assessment	X	X	X
Telephone Contact		X ³	X
Source Document and eCRF Completion	X		X

¹ The End of Study Visit should occur within 7 days after the subject treats up to his/her third headache or within 7 days after the completion of the 84-day treatment period, whichever occurs first.

² Subjects will return to the clinic at 4 and 8 weeks after the Screening Visit as necessary for a replacement dispenser.

³ Subjects will be contacted by telephone within 3 days of treating their 1st attack to answer any questions, assess if there are any problems with compliance or any concerning AEs.

9.0 ASSESSMENT OF SAFETY

9.1 General Guidelines

All AEs (NSAEs and SAEs), regardless of causality or severity, will be recorded in the subject's AE eCRF document according to Section 8.1.11. Appropriate medical intervention should be provided if required.

9.2 Definitions

The following definitions, developed in accordance with the International Committee on Harmonization (ICH) Clinical Safety Data Management Guidance for Industry, E2A, and 21 CFR Parts 312.32 and 812.3 will be used for the purpose of identifying AEs in this clinical study.

